#### **9.1.1.7 Clinic Visit 5: Day 120 (-7/+7 days)**

- Review and record any newly reported AEs since the site visit on Day 57 (medically-attended AEs, SAEs).
- Record concomitant medications and vaccinations, according to instructions in Section 7.6.
- Perform a symptom-directed physical examination (see Section 9.3.6).
- Measure vital signs (body temperature, pulse, blood pressure, see Section 9.3.6).
- Collect blood samples (see Table 1) for binding antibody testing to RBD of S protein of SARS-CoV-2 (~6 mL blood) and SARS-CoV-2 viral neutralizing activity (~6 mL blood). No testing of binding antibody to N protein of SARS-CoV-2 will be performed at this time point.
- Collect blood samples for CMI (~38 mL blood) from subjects of the CMI Subset.
- Instructions for the subject:
  - Remind the subject to call the site immediately to report the following:
    - If he/she experiences any concerning medical event.
    - Any medically-attended visits that are not routine visits for physical examination or vaccination, such as visits for hospitalization, an emergency room visit, or an otherwise unscheduled visit to or from medical personnel (medical doctor) for any reason.
    - Experience a serious medical event, have a change in overall health or be diagnosed with a new medical condition by a doctor. These should be reported regardless of the perceived relationship between the event and the trial vaccine.
  - Remind the subject to contact the site immediately if he/she has any of the symptoms suggestive of COVID-19. In addition, subjects will be messaged up to twice a week to provide a yes or no response to having COVID-19 symptoms. Those who respond “yes” will be contacted by trial staff for follow-up information, if the investigator considers the symptoms could potentially indicate a COVID-19 case (see Section 9.2.1 and Section 9.5).

- The subject should also be reminded to contact the site immediately if he/she had a positive SARS-CoV-2 test performed outside of the site, irrespective of whether they were symptomatic (COVID-19 illness) or asymptomatic at the time of the test.

#### **9.1.1.8 Clinic Visit 6: Day 211 (-7/+7 days)**

The assessments and procedures are identical to those performed during Clinic Visit 5 on Day 120, except for the below.

- Collect blood samples (see Table 1) for binding antibody testing to RBD of S protein of SARS-CoV-2 (~6 mL blood); SARS-CoV-2 viral neutralizing activity (~6 mL blood); and binding antibody testing to N protein of SARS-CoV-2 (~6 mL blood).
- Collect blood samples for CMI (~38 mL blood) from subjects of the CMI Subset.

#### **9.1.1.9 Phone Call: Day 302 (-7/+7 days)**

The purpose of this phone contact is to inquire about the subject's general well-being and to assess safety since the site visit on Day 211.

- During the phone call:
  - Review and record any newly reported AEs since the site visit on Day 211 (SAEs).
  - Record concomitant medications and vaccinations, according to instructions in Section 7.6.
  - If the subject reports by phone any concerning AEs, these should be followed-up either by a phone call(s) or by an unscheduled site visit based on the judgment of the investigator.
- Instructions for the subject:
  - Remind the subject to call the site immediately to report the following:
    - If he/she experiences any concerning medical event.
    - Any medically-attended visits that are not routine visits for physical examination or vaccination, such as visits for hospitalization, an emergency room visit, or an otherwise unscheduled visit to or from medical personnel (medical doctor) for any reason.
    - Experience a serious medical event, have a change in overall health or be diagnosed with a new medical condition by a doctor. These should be reported regardless of the perceived relationship between the event and the trial vaccine.
  - Remind the subject to contact the site immediately if he/she has any of the symptoms suggestive of COVID-19. In addition, subjects will be messaged up to twice a week to provide a yes or no response to having COVID-19 symptoms. Those who respond "yes" will be contacted by trial staff for follow-up information, if the investigator considers the symptoms could potentially indicate a COVID-19 case (see Section 9.2.1 and Section 9.5).

- The subject should also be reminded to contact the site immediately if he/she had a positive SARS-CoV-2 test performed outside of the site, irrespective of whether they were symptomatic (COVID-19 illness) or asymptomatic at the time of the test.

**9.1.1.10 End of Trial Visit: Day 393 (-0/+21 days) in CVnCoV subjects; for placebo subjects the visit (or phone call) might take place earlier as they will be withdrawn after trial unblinding**

For subjects who received CVnCoV, the end of trial visit will be performed on Day 393, 1 year after the last trial vaccine administration. For subjects who received placebo, the end of trial visit will be conducted after unblinding. If possible, this visit should also include subjects who prematurely discontinued vaccination during the trial. The following assessments should be performed:

- Review and record any newly reported AEs since the phone contact on Day 302 (SAEs).
- Record concomitant medications and vaccinations, according to instructions in Section 7.6.
- Record symptoms suggestive of COVID-19 or any confirmed COVID-19 case.
- Perform a complete physical examination, including height and weight (see Section 9.3.6).
- Measure vital signs (body temperature, pulse, blood pressure, see Section 9.3.6).

**9.1.2 All Other Subjects and subjects that, following unblinding, receive an authorized vaccine after having received at least one dose of CVnCoV**

Following enrollment of subjects into the Immunogenicity/Reactogenicity Subset (n=1,260), the remaining 1,260 subjects, 18 years of age and older, will be enrolled to this group.

Also, all subjects initially enrolled to the Immunogenicity/Reactogenicity Subset that receive an authorized vaccine following at least one dose of CVnCoV will be included in this group from the day when the authorized vaccine is administered (Schedule of Activities- Table 2).

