## 2 SCHEDULE OF ACTIVITIES

Subjects that received placebo in the trial following unblinding, will move from their initial schedule of activities (Table 1 or 2) to the End of Trial Visit (Table 2).

Subjects that, following unblinding, receive an authorized vaccine after having received at least one dose of CVnCoV will move to Table 2.

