- k. Binding antibodies to the RBD (receptor-binding domain) of the S (spike) protein and to the N (nucleocapsid) protein of SARS-CoV-2 will be measured by immunoassay. Viral neutralizing antibodies directed against SARS-CoV-2 will be measured by a functional activity assay. The N protein is not a component of the CVnCoV vaccine, but is being measured to determine serostatus of subjects to the SARS-CoV-2 virus (naïve or non-naïve to SARS-CoV-2); distinguish immune responses elicited by infection with SARS-CoV-2 from those induced by CVnCoV vaccination; and determine the occurrence of SARS-CoV-2 infection during the trial.
- l. Blood will be collected for measurement of antibody responses on Days 1, 29, 43, 57, 120 and 211, and cell-mediated immunity on Days 1, 29, 43, 57, 120, and 211 for a total volume of up to 318 mL.

**Table 2 Schedule of Trial Assessments and Procedures for All Other Subjects and for Subjects who, Following Unblinding, Receive an Authorized Vaccine After Having Received at least One Dose of CVnCoV**

(n=1,260)

	Vaccination Period				Follow-up Period			End of Trial
	Clinic Visit			Phone Call	Phone Call	Clinic Visit	Phone Call ii	Clinic Visit
Clinic Visit Number	1 a	2	3	-	-	4	-	5
Visit Window (days)	n/a	-3/+7	-3/+3	-3/+7	-7/+7	-7/+7	-7/+7	-0/+21
Trial Day	1	29	43	57	120	211	302	393
Vaccination Day (Reference for post-vaccination time points)	-	1	29+14	29+28	29+91	29+182	29+273	29+364
Visit Week (Wk) / Month (M)		Wk 4	Wk 6	Wk 8	M 4	M 7	M 10	M 13
Signed informed consent	X							
Inclusion/exclusion criteria	X							
Demographics	X							
Medical history	X							
Medication/vaccination history b	X							
Urine pregnancy test c	X	X						
Trial Vaccination								
Review criteria for delay or cancellation of trial vaccination d	X	X						
Administration of CVnCoV or control vaccine (observer-blinded)	X	X						
Safety Monitoring								
Physical examination e	X							X
Symptom-directed physical examination e		X	X			X		
Vital signs e,f	X f	X f	X			X		X
Collection of following AEs through the eDiary g :								
• Medically-attended AEs	X	X	X	X	X	X		

	Vaccination Period				Follow-up Period			End of Trial
	Clinic Visit			Phone Call	Phone Call	Clinic Visit	Phone Call i	Clinic Visit
Clinic Visit Number	1 a	2	3	-	-	4	-	5

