Visit Window (days)	n/a	-3/+7	-3/+3	-3/+7	-7/+7	-7/+7	-7/+7	-0/+21
Trial Day	1	29	43	57	120	211	302	393
Vaccination Day (Reference for post-vaccination time points)	-	1	29+14	29+28	29+91	29+182	29+273	29+364
Visit Week (Wk) / Month (M)		Wk 4	Wk 6	Wk 8	M 4	M 7	M 10	M 13
• SAEs and AESIs	X	X	X	X	X	X	X	X
• AEs leading to vaccine withdrawal or trial discontinuation	X	X	X	X	X	X	X	X
Concomitant medication/vaccination	X	X	X	X	X	X	X	X
COVID-19 Case Detection								
Case detection and collection of case information h	X	X	X	X	X	X	X	X
Antibody Testing								
Binding antibody to the N (nucleocapsid) protein and of SARS-CoV-2 i (~6mL blood)	X i		X			X		
Maximum blood volume collected by visit (mL)	6		6			6		
Trial End								X

AE: adverse event; AESI: adverse event of special interest; SAE: serious adverse event.

- Procedures to establish subject eligibility may be performed within 21 days prior to trial vaccine administration, unless otherwise indicated. If all information to establish eligibility is available, these procedures can be done on the same day as trial vaccine administration. Eligibility criteria should be reviewed and confirmed prior to trial vaccine administration.
- Medication/vaccination history taken within 6 months prior to enrollment should be recorded to establish eligibility.
- A urine pregnancy test will be performed within 24h prior to vaccination before each trial vaccination on Day 1 and Day 29 for women of childbearing potential.
- See Section 6.3 and Section 8.1 for an overview of the criteria leading to delay or cancellation of vaccine administration. In case of delay, the vaccination should take place within the allowed time windows, if feasible. The reasons for delay or cancellation should be documented in the subject chart.
- Physical examination and vital signs must be performed/measured by a qualified healthcare professional. See Section 9.3.6 for an overview of the required assessments.

- f. Vital signs will be measured pre- and post-vaccination prior to discharge. Subjects will be observed for at least 30 minutes following each vaccination. Vital signs must be within normal or clinically non-relevant abnormal ranges or have returned to pre-vaccination values for the subject to be discharged.

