### 4.2 Endpoints

#### 4.2.1 Primary Endpoints

##### Primary Safety Endpoints

- Occurrence, intensity and relationship of medically-attended AEs collected through 6 months after the second trial vaccination in all subjects.
- Occurrence, intensity and relationship of SAEs and AESIs collected through 1 year after the second trial vaccination in all subjects.
- Occurrence of fatal SAEs through 1 year after the second trial vaccination in all subjects.
- Occurrence of AEs leading to vaccine withdrawal or trial discontinuation through 1 year after the second trial vaccination in all subjects.
- Occurrence, intensity and duration of each solicited local AE within 7 days after each trial vaccination in a subset of subjects.
- Occurrence, intensity, duration of each solicited systemic AE within 7 days after each trial vaccination in a subset of subjects.
- Occurrence, intensity and relationship of unsolicited AEs occurring within 28 days after each trial vaccination in a subset of subjects.

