## 8.2 Withdrawal from the Trial

Subjects should be withdrawn from the trial in case any of the following situations occur:

- Continued participation jeopardizes the subject’s health, safety, or rights.
- The subject has experienced an AE that requires early termination because continued participation imposes an unacceptable risk to the subject’s health or the subject is unwilling to continue because of the AE. The reasons for not performing further safety or immunogenicity assessments should be documented.
- The subject did not return to the site and multiple attempts (a minimum of 3 attempts) to contact the subject were unsuccessful (lost to follow-up).
- The subject wishes to withdraw from the trial. The reason for withdrawal, if provided, should be recorded; this could include the availability of an approved COVID-19 vaccine.

All attempts should be made to determine the underlying reason for the withdrawal and, where possible, the primary underlying reason should be recorded (i.e., withdrawal due to an AE should not be recorded in the “voluntary withdrawal” category).

Any subject who prematurely terminates participation and who has received at least 1 trial vaccine dose will undergo the same procedures as for the end of trial visit, unless such procedures are considered to pose unacceptable risk to the subject.

After trial unblinding, i.e. after approval of study protocol version 3.0 and 4.0, all placebo subjects should be withdrawn at the earliest possible timepoint, if their originally planned End of Trial visit is later than February 2022 and will undergo the same procedures as for the End of Trial visit at their withdrawal visit. If a withdrawal visit cannot be scheduled for placebo subjects due to the pandemic setting, the end of trial assessment, i.e. collection of final safety data, can also be done by phone. In the e-CRF, the withdrawal reason for placebo subjects should be documented as “placebo subject withdrawn after trial unblinding”.

Discontinued or withdrawn subjects will not be replaced.

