#### **9.1.2.6 Phone Call: Day 302 (-7/+7 days) – after approval of protocols version 3 and 4 no longer to be performed in placebo subjects**

The purpose of this phone contact is to inquire on the subject’s general well-being and to assess safety since the last site visit on Day 211.

- During the phone call:
  - Review and record any newly reported AEs since the site visit on Day 211 (SAEs).
  - Record concomitant medications and vaccinations, according to instructions in Section 7.6.
  - If the subject reports by phone any concerning AEs, these should be followed-up either by a phone call(s) or by an unscheduled site visit based on the judgment of the investigator.
- Instructions for the subject:
  - Remind the subject to call the site immediately to report the following:
    - If he/she experiences any concerning medical event.
    - Any medically-attended visits that are not routine visits for physical examination or vaccination, such as visits for hospitalization, an emergency room visit, or an otherwise unscheduled visit to or from medical personnel (medical doctor) for any reason.
    - Experience a serious medical event, have a change in overall health or be diagnosed with a new medical condition by a doctor. These should be reported regardless of the perceived relationship between the event and the trial vaccine.

- Remind the subject to contact the site immediately if he/she has any of the symptoms suggestive of COVID-19. In addition, subjects will be messaged up to twice a week to provide a yes or no response to having COVID-19 symptoms. Those who respond “yes” will be contacted by trial staff for follow-up information, if the investigator considers the symptoms could potentially indicate a COVID-19 case (see Section 9.2.1 and Section 9.5).
- The subject should also be reminded to contact the site immediately if he/she had a positive SARS-CoV-2 test performed outside of the site, irrespective of whether they were symptomatic (COVID-19 illness) or asymptomatic at the time of the test.

**9.1.2.7 End of Trial Clinic Visit: Day 393 (-0/+21 days) in CVnCoV subjects; for placebo subjects the visit (or phone call) might take place earlier as they will be withdrawn after trial unblinding**

The end of trial visit will be performed on Day 393, 1 year after the last trial vaccine administration. If possible, this visit should include subjects who prematurely discontinued vaccination during the trial. The following assessments should be performed:

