10.5.6 Medically Attended AEs

Up to 6 months after second vaccination (or up to EOT, whatever is earlier), subjects are asked to confirm if they sought medical attention for an AE. Medically attended AEs are defined as AEs with medically-attended visits that are not routine visits for physical examination or vaccination, such as visits for hospitalization, an emergency room visit, or an otherwise unscheduled visit to or from medical personnel (medical doctor) for any reason. The start of a medically attended AE is defined by its start date, irrespective of the date medical attention was sought. A medically attended AE is considered as occurring up to 6 months after second trial vaccination if

$$\text{Start Date of AE} - (\text{Scheduled}) \text{ date of second vaccination} + 1 \leq 180 \text{ days.}$$

I.e. one month is defined as 30 days and the date of the scheduled second vaccination (Day 29) is used in case a subject only received the first vaccination.

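### The End of Trial checklist was written for Day 393 and does not prompt for medically-attended AEs in placebo subjects withdrawn before Day 211

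*Protocol*

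**What the plan says.** - **Endpoint.** Protocol 4.2.1 makes this a primary safety endpoint: "Occurrence, intensity and relationship of medically-attended AEs collected through 6 months after the second trial vaccination in all subjects".
- **Placebo path.** Protocol section 2 says that placebo subjects, after unblinding, "will move from their initial schedule of activities (Table 1 or 2) to the End of Trial Visit (Table 2". Section 8.2 adds that "all placebo subjects should be withdrawn at the earliest possible timepoint, if their originally planned End of Trial visit is later than February 2022", and lets the final assessment be done by phone if a visit cannot be scheduled.
- **EOT checklist.** Sections 9.1.1.10 and 9.1.2.7 carry the same AE item: "Review and record any newly reported AEs since the phone contact on Day 302 (SAEs".
- **The Day 302 call.** The heading of 9.1.2.6 says it is "after approval of protocols version 3 and 4 no longer to be performed in placebo subjects", and a footnote to Table 2 repeats this.
- **Schedule tables.** In Tables 1 and 2 the row "Medically-attended AEs" is marked up to Day 211 and is blank at Day 302 and EOT. The rows for SAEs and AESIs and for "AEs leading to vaccine withdrawal or trial discontinuation" are marked at EOT.
- **SAP 10.5.6.** "Up to 6 months after second vaccination (or up to EOT, whatever is earlier), subjects are asked to confirm if they sought medical attention".

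**The concern.** The EOT item makes sense for a visit on Day 393. By then the medically-attended AE window has closed, and a Day 302 call has taken place. The amended protocol uses the same visit as the exit contact for placebo subjects, and the item was not adapted. For these subjects the look-back starts at a call they do not have. If they leave before Day 211, the medically-attended AE window is still open, yet neither the checklist nor the EOT column mentions it.

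CVnCoV subjects stay on schedule and reach a Day 211 visit whose procedures do name medically-attended AEs. For the same stretch of follow-up, one arm has a specific prompt and the other relies on a general question. At stake is the between-arm comparison of a primary safety endpoint. Placebo events missed in this way would make CVnCoV look comparatively worse.

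**Working it through.** The plan gives no figure for this point, so the check compares the visit texts and then does day arithmetic. The nominal days are consistent with the schedule: 29 + 91 = 120, 29 + 182 = 211, 29 + 273 = 302, 29 + 364 = 393.

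**1. What each contact asks for**

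| Contact | AE categories named in the visit text | Medically-attended row marked |
|---|---|---|
| Day 120 | medically-attended AEs, SAEs | yes |
| Day 211 | as Day 120 (Subset) or as Day 43 (others): medically-attended AEs, SAEs | yes |
| Day 302 | SAEs | no |
| EOT | SAEs, counted from Day 302 | no |

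The visit texts name medically-attended AEs while the window is open and stop naming them once it has closed. That sequence fails only when EOT is moved ahead of Day 211.

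**2. Where the window ends.** SAP 10.5.6 counts an event if start date − second-dose date + 1 ≤ 180. With the second dose on Day 29, the last counted day is 29 + 179 = Day 208.

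**3. Length of the unprompted interval.** For a placebo subject whose last contact was Day 120, withdrawn on day w before the Day 211 visit, the interval is min(w, 208) − 120:

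| Withdrawn on | Interval (days) | Share of the 180 days after dose 2 |
|---|---|---|
| Day 150 | 30 | 17% |
| Day 180 | 60 | 33% |
| Day 208 or later, before the Day 211 visit | 88 | 49% |

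Counted from the first dose, the maximum is 88/208 = 42%. If withdrawal comes between Day 57 and Day 120, the interval starts at Day 57 and is shorter than 120 − 57 = 63 days. After the Day 211 visit it is nil.

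**4. Who could be affected.** A planned Day 393 after 28 February 2022 means Day 1 after 28 February 2022 − 392 days = 1 February 2021. The earliest such subject (Day 1 on 2 February 2021) reaches Day 211 on 31 August 2021. Approval, withdrawal and last-enrolment dates are not given, so the withdrawal dates below are assumptions. Day 211 has been reached if Day 1 is no later than the withdrawal date − 210 days.

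| Assumed withdrawal date | Within the 8.2 group, affected if Day 1 is after |
|---|---|
| 11 Aug 2021 (version date of protocol 4.0) | 1 Feb 2021 (the whole group; the 210-day limit is 13 Jan 2021) |
| 30 Sep 2021 | 4 Mar 2021 |
| 31 Oct 2021 | 4 Apr 2021 |
| 22 Dec 2021 (version date of protocol 5.0) | 26 May 2021 |

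The length also varies within a row. At 11 August 2021, a subject with Day 1 on 2 February 2021 passed Day 120 on 1 June and has 71 unprompted days. One with Day 1 on 14 April 2021 is at Day 120 that same day and has none.

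**5. Whether it reaches the main tables.** SAP 10.10 censors both arms for safety from the day after unblinding or receipt of an authorized vaccine, whichever is earlier. SAP 10.5.6 dates a medically-attended AE by its onset. An event between Day 120 and censoring therefore still counts. In a CVnCoV subject it can be picked up at Day 211; in a placebo subject withdrawn first there is no listed prompt for it. Censoring removes only later events, so it shortens the interval without closing it.

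**The case against.** The strongest reply is that the protocol already requires these events to be collected. Section 9.3.2 sets collection through 6 months for all subjects. Section 9.3.3.2 requires non-directive questioning about serious and non-serious AEs at each visit, with recording of whatever meets 9.3.2. Appendix 10 repeats the duty, and its example question already looks back to the last contact. The eDiary serves as a memory aid for these events, and subjects are told to report medical visits to the site. SAP 10.5.6 describes the question as asked up to an earlier EOT.

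This stands against two stronger readings. A reader might infer that medically-attended AEs are never asked for in withdrawn placebo subjects; the rules just listed contradict that. A reader might also infer that the EOT contact records only SAEs; Tables 1 and 2 mark AESIs and AEs leading to withdrawal or discontinuation there, so the checklist is narrower than its own table. The reply does not remove the asymmetry: the general routes exist in both arms, while the specific prompt before the window closes reaches only subjects who attend Day 211. Nor does any EOT instruction supply the question that SAP 10.5.6 describes.

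The other objections concern size. Protocol 5.4 and 8.2 tie placebo exits to approval of versions 3.0 and 4.0, whose dates are not given, and the amendment history lists the section 8 placebo withdrawal procedure under version 5.0. Exits may therefore have come well after August 2021. SAP 12.6.7 speaks of massive data loss through censoring, so many subjects' intervals may be short or nil in the main tables. Safety is analysed descriptively, without formal testing. All of this limits the size of the effect; none of it makes the checklist correct.

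Section 8.2 applies EOT procedures to early leavers in either arm. They meet the same checklist, but they create no built-in difference between arms.

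**Conclusion.** The checklist and the EOT column conflict with 9.3.2, 9.3.3.2, Appendix 10 and SAP 10.5.6 for placebo subjects withdrawn before their Day 211 visit. Medically-attended AEs before unblinding could be under-ascertained in placebo relative to CVnCoV. The documents do not support saying that the placebo rate is biased downward: the general routes may capture the events, and the number of affected subjects is unknown.

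The interval is at most about 88 days on nominal visit days with the second dose on Day 29; visit windows move this by some days. It ends at each subject's own censoring date in the main tables and is nil for anyone past Day 211. Depending on withdrawal dates, the affected group could be most of the withdrawn placebo subjects, or few or none. The point is worth correcting because it touches a primary safety endpoint and the remedy is small.

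**What to change.** In 9.1.1.10, 9.1.2.7 and the EOT column of Tables 1 and 2, and for the phone version in 8.2:

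- Set the look-back to the last completed visit or call.
- List SAEs, AESIs and AEs leading to vaccine withdrawal or trial discontinuation.
- Add medically-attended AEs when the EOT contact falls before the Day 211 visit.

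For placebo subjects already withdrawn before Day 211, query the site for medically-attended AEs since their last contact.

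The cost is protocol wording, one extra question at a contact already held, and a limited set of site queries for subjects who have left.
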